4. SAMPLE SIZE AND POWER CALCULATION

The sample size for this study will be 40 subjects. This sample size is based on historical experience with the proposed analysis. A sample size of 40 subjects will be sufficient for meeting the endpoints described herein.

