5.1.2 Diagnostic Imaging Endpoints

Diagnostic performance of pegsitacianine will be assessed by calculating sensitivity, specificity, NPV, and PPV of pegsitacianine in detecting tumor containing tissue. The *ex situ* fluorescence status (any fluorescence vs. no fluorescence) of collected SOC and pegsitacianine guided specimens, as well as lymph nodes, will be compared to histological analyses of the collected specimens. Sensitivity and specificity for detecting tumor-containing tissue versus normal tissue

will be evaluated using tissue specimen fluorescence and the corresponding pathological outcomes.

True/false/negative/positive definitions are as follows:

- False positive is defined as fluorescence was observed on the sample but the sample was not found to have tumor via pathology.
- False negative is defined as no fluorescence was observed on the sample but the sample was found to have tumor via pathology.
- True positive is defined as fluorescence was observed on the sample and the sample was found to have tumor via pathology
- True negative is defined as no fluorescence was observed on the sample and the sample was found not to have tumor via pathology.

Pegsitaricaine sensitivity and PPV will be calculated using the following equations:

$$\text{Sensitivity} = \frac{\text{\# of True Positive Specimens}}{\text{\# of True Positive Specimens} + \text{\# of False Negative Specimens}}$$

$$PPV = \frac{\# \text{ of True Positive Specimens}}{\# \text{ of True Positive Specimens} + \# \text{ of False Positive Specimens}}$$

Pegsiraniline specificity values and NPV will be calculated using the following equations:

$$\text{Specificity} = \frac{\text{\# of True Negative Specimens}}{\text{\# of True Negative Specimens} + \text{\# of False Positive Specimens}}$$

$$NPV = \frac{\# \text{ of True Negative Specimens}}{\# \text{ of True Negative Specimens} + \# \text{ of False Negative Specimens}}$$

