5.1.3 Fluorescence Endpoints

Specimen-to-background (SBR) ratios will also be calculated using white light and NIR images of both SOC and pegsitanine guided specimens. SBRs will be calculated using *ex situ* images of collected specimens. The equation for calculating SBR is listed below.

$$SBR = \frac{\text{Mean Fluorescence Intensity (Specimen)}}{\text{Mean Fluorescence Intensity (Normal Tissue)}}$$

Note: tumor-to-background (TBR) ratios are equivalent to SBR, but only relevant for specimens with tumors.

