7.10.3 Exploratory Analyses

7.10.3.1 Analysis of Fluorescence Intensity

A summary of MFI for the tumor (or suspected tumor), MFI for the normal background tissue, and TBR will be provided by Part and overall for each pathology result (tumor vs. no tumor). This summary will be at the specimen level, meaning each subject may have multiple specimens.

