7.10.3.2 ROC Analysis

In this pilot study we are assuming that any fluorescence is indicative of tumor presence. To assess how the amount of observed fluorescence (e.g., the SBR or TBR) may affect the diagnostic accuracy of pegasitacianine, a receiver operating characteristic (ROC) analysis will be performed on all specimens using the observed thresholds of SBR and TBR. The corresponding ROC curve

will be provided along with the area under the curve (AUC) and the 95% confidence interval of the AUC.

There is potential for within-subject correlation to bias our estimates of pegsitacianine's diagnostic accuracy. To assess this issue, an ROC curve will be constructed from a mixed model that clusters specimens by the subject they originated from. We will compare the AUC of the mixed effects ROC curve to the standard ROC curve to assess if within-subject correlation is causing significant bias in our analyses. If it is determined that significant bias has been introduced, additional analyses on secondary endpoints may be performed to assess the diagnostic accuracy of pegsitacianine.

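### The planned AUC comparison cannot show whether within-patient correlation harms the accuracy estimates; patient-clustered intervals should replace it

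*SAP*

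**What the plan says.** SAP 7.10.3.2 plans a standard ROC curve; its "analysis will be performed on all specimens using the observed thresholds of SBR and TBR". It reports the AUC with a 95% confidence interval but names no interval method. It then says that correlation within a subject could bias the accuracy estimates, and proposes a check: "an ROC curve will be constructed from a mixed model that clusters specimens by the subject they originated from". Next comes the comparison, "We will compare the AUC of the mixed effects ROC curve to the standard ROC curve", and its consequence: "If it is determined that significant bias has been introduced, additional analyses on secondary endpoints may be performed". Protocol 9.6 describes the same check with no more detail on the model.

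Neither document gives the response variable, the covariates, the random-effect structure, whether predictions include the subject effect, or the difference that would count as significant bias.

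Several specimens per patient are expected. SAP 7.10.3.1 describes its specimen-level summary as "meaning each subject may have multiple specimens". The secondary endpoints rest on a binary ex situ call, "fluorescence status (any fluorescence vs. no fluorescence" (SAP 5.1.2). Their intervals are Clopper-Pearson, computed on specimens (SAP 7.10.2.1; exact intervals in protocol 9.4).

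**The concern.** This comparison is the only analysis in either document that addresses correlation between specimens from one patient. AUC depends on ranks alone, and a mixed model either leaves the ranks of SBR unchanged or changes them for reasons unrelated to bias in the standard AUC. A zero difference could then be read as evidence that clustering is harmless, and a positive one as evidence of bias where none exists.

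At stake is the precision claimed for sensitivity, specificity, PPV, NPV and AUC. Protocol 9.1 says the trial should inform power calculations for later studies, and specimen-level intervals that are too narrow would carry over into that planning.

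**Working it through.** **Inputs from the documents.** There are 40 patients (SAP 4: "The sample size for this study will be 40 subjects"). The ROC score is SBR. TBR "ratios are equivalent to SBR, but only relevant for specimens with tumors" (SAP 5.1.3), so only SBR has values in both pathology classes. The documents give no AUC, intraclass correlation (ICC), bias cut-off or specimen count, so there is no planned figure to reproduce.

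**Assumed inputs.** Set A: 6 specimens per patient, log-SBR shift 1.2 SD. Set B: 2 to 8 specimens, shift 1 SD. Each used 40 patients, 200 runs per setting, and a random-intercept logistic model fitted by 21-point Gauss-Hermite quadrature with empirical-Bayes patient effects.

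**Step 1: fixed part only.** The model is logit P(tumor) = b0 + b1·SBR + u_i. With b1 > 0, b0 + b1·SBR increases with SBR, so every tumor/non-tumor pair is ordered as SBR orders it. The AUC difference is therefore exactly 0 for any correlation. It was 0.0000 in every simulated run with a positive slope. A negative slope only reverses the ranking and gives 1 − AUC.

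**Step 2: patient effect included.** The estimate of u_i comes from the pathology results being predicted.

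| Setting (assumed) | Mean rise over the standard AUC |
|---|---|
| No clustering, set A | 0.010 |
| No clustering, set B | 0.764 to 0.779, +0.015 |
| Only tumor fraction differs between patients, set A | 0.057 |
| Only pathology clustered (intercept SD 1), set B | 0.761 to 0.862, +0.10 |
| SBR ICC 0.3 to 0.5, set A | 0.10 to 0.13 |
| SBR ICC 0.5 only, set B | 0.10 |
| Pathology and SBR both clustered, set B | 0.15 |
| Useless marker, clustered pathology, set B | 0.500 to 0.820, +0.32 |

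The last row shows the mechanism: SBR carries no information there, so the whole gain comes from the patients' own pathology.

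**Step 3: SBR as the response.** Take total SD 1, shift 1.2 and ICC 0.3.
- Pooled AUC = Φ(1.2/√2) = 0.802.
- Within-patient AUC = Φ(1.2/√(2 × 0.7)) = Φ(1.2/√1.4) = 0.845.

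The gap of 0.043 is a change of estimand. In set B the within-patient AUC exceeded the standard one by 0.077 at ICC 0.5, and by about 0 to 0.002 when SBR was not clustered. A pooled binormal AUC from the model differed by about 0 to −0.003 when SBR was normal and by −0.066 when it was skewed, which is an effect of distributional form. Some of these fits gave convergence or boundary warnings, so the simulated figures in this step are approximate.

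**Step 4: what clustering does to the planned estimates.** In 2,000 runs per setting with set A's shift (true AUC 0.802), the standard AUC stayed at 0.80 throughout. With 6 specimens per patient, a 95% interval that treats specimens as independent covered about 94% at ICC 0, 89 to 93% at ICC 0.3 and 85 to 91% at ICC 0.5. A clustered nonparametric variance gave 92 to 94%, with intervals up to 1.31 times as wide.

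For the proportions, the approximate design effect is 1 + (m − 1) × ICC, with m specimens per patient in the denominator:
- m = 3, ICC 0.1: 1 + 2 × 0.1 = 1.2; width ratio √1.2 ≈ 1.1.
- m = 8, ICC 0.5: 1 + 7 × 0.5 = 4.5; width ratio √4.5 ≈ 2.1.
- m = 1: the design effect is 1. Sensitivity would therefore be little affected if most patients supply one tumor specimen.

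A comparison of two AUC point estimates carries no information about these widths.

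**The case against.** The strongest reply is that the SAP does not say which mixed model it means. The exact zero in step 1 needs a logistic model of pathology with SBR as the only covariate and a positive slope. With SBR as the response, a within-patient comparison does respond to patient-level shifts in SBR. A reader might infer that the check is bound either never to fire or to fire falsely. The documents do not support that: they fix neither the model nor a cut-off, and the follow-up is optional.

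The reach is also limited. The analysis is exploratory, the trial is not powered for hypothesis testing (protocol 9.1), and the primary endpoint is counted per patient. Protocol section 9 allows further analyses and SAP 7.10.3.4 allows post-hoc work on sensitivity and specificity, so re-analysis does not depend on this trigger. The SAP names no interval method for the AUC, so the coverage figures illustrate an unclustered choice and do not describe a stated one.

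All of this stands and limits the claim, but it does not rescue the check. None of the readings examined measures bias in the planned estimates, and leaving the model and cut-off open lets the analyst choose among them after seeing the results.

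**Conclusion.** The point holds in a limited form. As written, the comparison cannot show whether clustering harms the planned estimates. Under the usual logistic mixed model the difference is exactly zero from the fixed part. With the patient effect it is about 0.01 without clustering and 0.06 to 0.15 with it, while the standard AUC is not itself biased. The exact zero is algebra; the other figures rest on assumed specimen counts, SBR separation and correlation. With SBR as the response, the difference reflects a change of quantity or distributional form.

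The check also looks in the wrong place: it examines SBR point estimates, while the secondary endpoints use a binary call and the main cost of clustering is interval width.

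A reader might further infer that the larger mixed-model AUC would be presented as the agent's accuracy. The SAP does not say so; it attaches the reported AUC and interval to the standard curve.

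**What to change.** - Delete the AUC comparison and its trigger from SAP 7.10.3.2 and protocol 9.6.
- Report the one empirical AUC of SBR with a 95% interval from a patient-level bootstrap or the nonparametric variance for clustered data.
- In SAP 7.10.2.1 and protocol 9.4, replace the specimen-level Clopper-Pearson intervals for sensitivity, specificity, PPV and NPV with patient-clustered 95% intervals, fixed in advance. Deleting the check without this step would leave those endpoints with no allowance for correlation.
- State what will be done if a proportion is 0 or 100%, where a bootstrap interval has no width. One option is Clopper-Pearson on the number of contributing patients.
- If a within-patient AUC is wanted, report it beside the pooled AUC and label it as a different quantity.
- If only the SAP is changed, record the change in SAP section 8, which now lists no departures from the protocol.

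The cost is a small amount of code and somewhat wider intervals: up to about 1.3 times for the AUC in the settings above, and 1.1 to 2.1 times for proportions with 3 to 8 specimens per patient in the denominator and ICC 0.1 to 0.5, all assumed. No new data are needed, and SAP 7.1 allows updates before database lock.

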7.10.3.3 Camera System Analysis

An analysis on diagnostic results by camera system will be performed. 2x2 incidence tables comparing the true/false negative/positive results will be constructed for each camera system, and compared via the Breslow-Day test to assess if there is any effect of camera system on diagnostic results (e.g. to test if the common odds-ratio of each incidence table is equivalent across camera types). A summary including the diagnostic true/false negative/positive numbers and rates for each camera system, sensitivity, specificity, and p-value of this analysis will be provided.

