### 1.2 Pegsitacianine Clinical Trial Background

Four clinical studies have been performed or are currently enrolling using pegsitacianine. The study *ON-1001: Image-Guided Surgery for Tumor Detection in Solid Tumors Using the pH Activated Micellar Probe ONM-100: The SHINE Study*, was conducted in the Netherlands at the

University Medical Center Groningen and completed in 2019. The completed Phase 2 study, *ON-1002: A Study to Evaluate ONM-100, an Intraoperative Fluorescent Imaging Agent for the Detection of Cancer* ([NCT03735680](#)) was a multicenter trial in the United States. *ON-1004* was a Phase 1 normal healthy volunteer study to further evaluate the pharmacokinetic profile of pgsitacianine. *ON-1003: A Phase 2, Single-Dose, Open-Label Study to Evaluate Diagnostic Performance and Safety of Pgsitacianine, an Intraoperative Fluorescence Imaging Agent for the Detection of Peritoneal Metastases, in Patients Undergoing Cytoreductive Surgery* ([NCT04950166](#)) is an ongoing multicenter study in the United States.

The purpose of the ON-1001 study was to investigate the safety, pharmacokinetics and feasibility of pgsitacianine as an intraoperative imaging agent for the detection of tumors and metastatic lymph nodes in solid cancers. Additionally, the study investigated the optimal dose range of pgsitacianine for an adequate tumor-to-background/contrast-to-noise ratio of fluorescence obtained intraoperatively and with *ex vivo* specimens using indocyanine green (ICG) compatible cameras and imaging devices. A single pgsitacianine dose was administered [REDACTED] as a one to five-minute infusion to patients in five dose cohorts [REDACTED] with three patients per cohort in Phase 1A, and 15 patients at a dose of [REDACTED] in Phase 1B. Near-infrared (NIR) imaging was conducted intraoperatively, on the back table, and postoperatively of the primary tumor, lymph nodes, and pgsitacianine guided biopsies. Additionally, the bread loaf slices from the primary tumor were imaged postoperatively. The median [REDACTED] value from all [REDACTED] with an interquartile range of 3.1. Additionally, pgsitacianine demonstrated a sensitivity of 100% across all tumor types tested with a specificity of 75% and [REDACTED]

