2. STUDY OBJECTIVES

2.1 Objectives and Endpoints

The primary objective of this study is to investigate whether pegasitacianine can detect clinically significant events (CSEs) at the patient level, which include:

1. The detection of disease that cannot be detected using standard procedures during the surgical resection of lung malignancies
2. The detection of synchronous lesions
3. The detection of positive surgical margins following primary tumor resection
4. Tumor-negative standard of care (SOC) biopsies

Table 1. Objectives and Endpoints

Objectives	Endpoints
Primary Objective	Primary Endpoint
The primary objective of this study is to investigate whether pegasitacianine can detect clinically significant events (CSEs) at the patient level.	Rate of CSEs, which include: 
1. The detection of disease that cannot be detected using standard procedures during the surgical resection of lung malignancies2. The detection of synchronous lesions3. The detection of positive surgical margins following primary tumor resection4. Tumor-negative standard of care (SOC) biopsies

Secondary Objectives	Secondary Endpoints
Determine sensitivity, specificity, negative predictive values (NPPV), and positive predictive values (PPV) of the imaging agent at the level of the individual specimens, including lymph nodes.	Sensitivity, specificity, negative predictive values (NPV), and positive predictive values (PPV) at the specimen-level.
Evaluate safety and toxicity of pegsitacianine.	Incidence of TEAEs and SAEs, abnormalities in lab values, vital signs, or ECG results.
Exploratory Objectives	Exploratory Endpoints
Assess the how the SBR affects the diagnostic accuracy of pegsitacianine in detection of metastatic disease vs. normal tissue.	ROC analysis across various tumor-to-background ratio fluorescence thresholds.
Effect of camera system on diagnostic results.	Diagnostic results across various camera systems.
Assess amount of fluorescence shown in various types of specimens.	Mean fluorescence intensity and Specimen-to-background ratio

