3. STUDY DESCRIPTION

3.1 Study Design

This Phase 2 study will be an interventional, open-label, single arm trial where each patient is his/her own “intrapatient” control. All patients will receive a single █ mg/kg dose of pegsitacianine administered █ prior to standard of care (SOC) surgery. The study will be conducted in two Parts. Part 1 will enroll patients undergoing minimally invasive procedures (i.e., video-assisted thorascopic surgery [VATS] or robotic surgery). Part 2 will be opened at the discretion of the Sponsor and include patients undergoing open thoracotomy for the removal of their disease. [Note: Part 2 was not opened to enrollment.]

Patients will have a biopsy confirmed diagnosis, or a high clinical suspicion of a lung malignancy based on CT and/or PET imaging. A total of up to 40 patients will be enrolled in this trial. The sponsor reserves the right to perform an interim analysis following early enrollment (n ≤ 10 subjects) to determine the feasibility and benefit of pegsitacianine as an adjunct to SOC surgery.

The surgeon will attempt to perform their SOC resection of visible tumors. If the tumor is unable to be located under standard white light conditions, an appropriate near-infrared (NIR) imaging device may be used to aid in the location of the primary tumor. Localization of the primary tumor using NIR imaging in conjunction with pathology confirmed presence of disease will be considered a clinically significant event.

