7.5 Adjustment for Multiplicity

There are no planned adjustments for multiple endpoints or analyses.

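### The Breslow-Day camera comparison tests only equality of odds ratios, so it can miss a sensitivity/specificity trade-off that leaves the odds ratio nearly unchanged, and it has no value if FP x FN = 0 on every camera

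*SAP*

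**What the plan says.** SAP Table 1 (section 2.1) has an exploratory objective on the effect of the camera system, with the endpoint "Diagnostic results across various camera systems". SAP 7.10.3.3 carries this out with one table of true/false positives and negatives per camera, to be "compared via the Breslow-Day test to assess if there is any effect of camera system on diagnostic results". A parenthesis opening with e.g. gives the hypothesis: "to test if the common odds-ratio of each incidence table is equivalent across camera types". The output is the counts and rates per camera, sensitivity, specificity and one p-value. No other between-camera comparison is specified, and nothing is said about zero cells.

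Four other places bear on this:
- SAP 7.10.3.2 gives the positivity rule: "In this pilot study we are assuming that any fluorescence is indicative of tumor presence".
- SAP 7.10.3.1 confirms that specimens are clustered: "This summary will be at the specimen level, meaning each subject may have multiple specimens".
- SAP 3.1 notes that "Part 2 was not opened to enrollment", so only cameras used in minimally invasive surgery are compared.
- SAP 7.5 states "There are no planned adjustments for multiple endpoints or analyses".

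**The concern.** The stated aim is broad and the test is narrow. The diagnostic endpoints in SAP Table 1 are sensitivity, specificity, PPV and NPV. The odds ratio is not among them, yet it is the only quantity Breslow-Day compares. Two cameras can differ widely on both sensitivity and specificity and still share one odds ratio.

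The positivity rule makes that pattern plausible. If one camera shows fainter fluorescence than another (an assumption), it calls more specimens positive, so sensitivity rises and specificity falls. A large p-value, presented as a check for a camera effect of any kind, could then be read as reassurance beside rates that plainly differ. If no camera has a false negative, there would be no p-value at all, however far apart the specificities were.

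**Working it through.** The plan gives no alpha, power or specimen count for this analysis, so there is no figure to reproduce. Specimen counts, camera numbers and accuracies below are assumptions. Alpha is taken as 0.05, in line with the 95% intervals in SAP 7.2. Pairs are sensitivity/specificity in per cent.

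**Formulas**
- Odds ratio on one camera: OR = (TP x TN)/(FP x FN) = [Se/(1-Se)] x [Sp/(1-Sp)].
- Common odds ratio over cameras (Mantel-Haenszel): sum(TP x TN/n) / sum(FP x FN/n).
- Breslow-Day: sum of (TP - E)^2/V, where E is the expected TP given the margins and the common OR, and V is its variance. It is referred to chi-square on K-1 degrees of freedom for K cameras.

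**1. Trade-off at equal odds ratio.** With 20 tumor and 20 normal specimens per camera:
- Camera A, 95/50: TP 19, FN 1, FP 10, TN 10; OR = 19 x 10/(10 x 1) = 19.
- Camera B, 50/95: TP 10, FN 10, FP 1, TN 19; OR = 10 x 19/(1 x 10) = 19.
- Breslow-Day: chi-square 0, p = 1.00. Fisher: 19/20 v 10/20, p = 0.003 for sensitivity, and the same for specificity.

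More specimens do not help. For 90/60 v 60/90 both odds ratios are 9 x 1.5 = 13.5. Breslow-Day gives p = 1.00 at 40+40, 100+100 and 1000+1000 specimens per camera, while Fisher on each measure gives p = 0.0038, 1.2e-6 and 1.3e-56.

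**2. Rejection rates.** Simulation with two cameras and independent specimens; 20 tumor and 60 normal per camera except in the last row. Breslow-Day is at 0.05, and separate Fisher tests are at 0.025 each.

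| Pattern | Camera A v B | OR A v B | Breslow-Day | Fisher pair |
|---|---|---|---|---|
| Threshold shift on one ROC curve | 90.7/75 v 76.4/90 | about 29 v 29 | 4.9% | 43.4% |
| Large trade-off, equal OR | 90/60 v 60/90 | 13.5 v 13.5 | 5.6% | 96.0% |
| Ten-point trade-off | 90/75 v 80/85 | 27 v 22.7 | 4.4% | 16.7% |
| Specificity only, large | 90/90 v 90/50 | 81 v 9 | 48.3% | 99.7% |
| Sensitivity only, large | 90/90 v 60/90 | 81 v 13.5 | 41.2% | 37.2% |
| Worse on both | 90/85 v 80/75 | 51 v 12 | 28.9% | 16.0% |
| Trade-off that changes the OR (40+40) | 95/80 v 60/85 | 76 v 8.5 | 65% | 94% |

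The first row uses Sp = Phi(t) and Se = Phi(2.0 - t), that is, equal-variance normal signals with AUC 0.92.

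**3. When the statistic does not exist.** The denominator sum(FP x FN/n) is 0 when FP x FN = 0 on every camera.
- Example: 20/20 tumors detected on both cameras, specificity 45/60 v 57/60. Breslow-Day has no value. Fisher for specificity gives p = 0.004, and the exact 95% intervals are 62-85% and 86-99%.
- With FN = 0 on one camera only, the test can be calculated. TP 20, FN 0, FP 8, TN 22 against TP 17, FN 3, FP 6, TN 24 gives chi-square 2.05, p = 0.15. The condition must hold on every camera.

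When every camera has some false positives, the chance is about Se^D, where D is the total number of tumor specimens:

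| Sensitivity | D = 40 | D = 20 |
|---|---|---|
| 70% | 0.70^40 < 0.0001% | 0.08% |
| 90% | 1.5% | 12.2% |
| 95% | 12.9% | 35.8% |
| 98% | 44.6% | 66.8% |

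Cameras with no false positives raise these figures. Over two or three cameras, specificity 60-90%, and D = 40 with 40 to 120 normal specimens, the range is 1.5-9% at 90% sensitivity, 13-26% at 95% and 45-57% at 98%.

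**4. Does a direct comparison work in the zero-cell example?** The Newcombe interval combines Wilson intervals. For specificity these are 57/60: 0.863-0.983 and 45/60: 0.628-0.842. The difference is 0.20, with lower limit 0.20 - sqrt(0.087^2 + 0.092^2) = 0.07 and upper limit 0.20 + sqrt(0.033^2 + 0.122^2) = 0.33. For sensitivity, 20/20 v 20/20, the Wilson lower limit is 1/(1 + 3.84/20) = 0.84, so the difference is 0 with interval -0.16 to 0.16. Both exist.

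**The case against.** The SAP names the odds-ratio hypothesis in its own parenthesis and prints sensitivity and specificity per camera beside the p-value, so an attentive reader would see a large trade-off. SAP 7.10.3.4 allows post-hoc work on further covariates and Protocol 9 allows additional analyses. Protocol 9.1 says the study is not powered for testing. All of this stands and keeps the point small. It does not cure it, because the parenthesis is only an example, the broad aim remains, and the other provisions are optional.

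Three stronger readings are tempting, and none is supported:
- **That Breslow-Day is blind to every trade-off.** It is not: 95/80 v 60/85 changes the odds ratio from 76 to 8.5 and is detected about 65% of the time at 40+40.
- **That the p-value will probably be missing.** The case for very high sensitivity rests on one line of Protocol 1.2, which says the first-in-human study "demonstrated a sensitivity of 100% across all tumor types tested with a specificity of 75" per cent. The tumor types there did not include lung (Protocol 4.3). The only accuracy threshold set for this trial is 70% (Protocol 3.1), where the zero-cell problem is negligible. Lymph nodes also count as specimens here (SAP 5.1.2), and Protocol 1.2 says a later study asked whether their detection could be improved.
- **That separate comparisons are always better.** Breslow-Day does better when one camera is worse on both measures, and slightly better in the sensitivity-only row.

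The Fisher rates also assume independent specimens and balanced camera use. For the threshold shift, direct intervals adjusted for clustering (97.5% level, one tumor and three normal specimens per subject) detected 50%, 42% and 33% at intraclass correlations of 0, 0.2 and 0.4 with 20 subjects per camera. With a 34/6 split they detected 25%, 21% and 18%, against 5-8% for Breslow-Day. The advantage remains but is smaller than the largest contrasts in the table.

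**Conclusion.** The concern holds, as a minor point. The specified test does not do the job the SAP gives it. Against a trade-off that leaves the odds ratio (nearly) unchanged it rejects at about its alpha level at any sample size, and it is undefined when FP x FN = 0 on every camera, for which the SAP has no rule. The algebra behind both statements needs no assumption. How often either would arise does depend on assumptions, since the documents give no specimen counts, accuracies or correlations by camera. No decision depends on this p-value, and the primary and secondary analyses are untouched.

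**What to change.** In SAP 7.10.3.3:
- Compare cameras directly on sensitivity (tumor-positive specimens) and on specificity (tumor-negative specimens). Give exact 95% intervals per camera, and between-camera differences with a 95% interval that tolerates zero cells, such as the Newcombe score interval.
- Label these descriptive, for two reasons. They ignore clustering by subject. Camera may also be confounded with site and surgeon: up to five centers take part, the surgeon calls the fluorescence, and SAP 7.6 plans no center adjustment. A clustering adjustment is optional. Its absence can matter for specificity: with an assumed 1 to 11 normal specimens per subject, unadjusted difference intervals covered 81-83% at an intraclass correlation of 0.2 and 69-70% at 0.4.
- If Breslow-Day is kept as a supplement, restate its aim as equality of diagnostic odds ratios across cameras. Report it as not calculable when FP x FN = 0 on every camera, and say that a non-significant result is not evidence of no camera effect.

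The cost is SAP wording and a little programming; SAP 7.1 allows updates before database lock. There would be two exploratory comparisons instead of one, with no multiplicity adjustment planned. Intervals will be wide: for 18/20 v 16/20 the Wilson intervals are 0.699-0.972 and 0.584-0.919, so the difference of 10 points runs from 0.10 - sqrt(0.201^2 + 0.119^2) = -0.13 to 0.10 + sqrt(0.072^2 + 0.216^2) = 0.33. Dropping Breslow-Day altogether would lose some power when one camera is worse on both measures (about 29% v 16% for 90/85 v 80/75 above).
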